## **8.0. OBJECTIVES**

### **8.1. OBJECTIVE 1 (FRCT)**

To assess the capability of the implantable vascular monitoring device in the early postoperative period of kidney transplant patients.

### **8.2. OBJECTIVE 2 (FRCT)**

To assess the research methods used to compare vascular monitoring device with the standard care and to estimate surgical outcome measures essential to inform the sample size calculation for the definitive planned RCT.

### **8.3. OBJECTIVE 3 (FRCT)**

To assess the availability of research resources, management support, potential barriers and challenges for the definitive planned RCT.

### **8.4 OBJECTIVE 4 (EMBEDDED QUALITATIVE STUDY)**

To assess the acceptability of vascular monitoring device in clinical practice and get suggestions on the protocol development of the definitive planned RCT

## **9. TRIAL DESIGN**

Mixed methodology two-arm feasibility randomised controlled trial with an embedded qualitative study.

## **10. RECRUITMENT**

The participants will be recruited from the patients undergoing kidney transplant surgery at Southwest transplant centre, UHPNT. The transplant surgical fellow will review the patients, recruit the eligible participants and obtain their consent for the study. The normal care pathway followed at our transplant unit is designed in line with the unpredictable nature of the specialty. We are offered organs by NHS Blood and Transplant (NHSBT) from deceased donors with a notice period of 12-14 hours. The kidney transplant recipient is admitted to the hospital about 8-10 hours before the surgery. The patient is prepared and consented to surgery during this interval. The patient is then moved to the operation theatre for implantation. Afterwards, the patient is transferred to the renal ward for postoperative care. All patients receive standard care clinical observation to monitor their graft function. In addition to the standard care clinical observation, the clinician looking after the patients may request additional departmental ultrasound scans in the first 72 hours depending on the graft function and the condition of the kidney transplant recipient.

There will be no difference in the recruitment process, consent, and the postoperative care of kidney transplant patients with the monitoring device or with the standard care clinical observation.

## **11. TRIAL PARTICIPANTS**

The participants of the study will consist of the patients who will have kidney transplant surgery with or without the implantable vascular monitoring device during the study duration at the Southwest transplant centre UHPNT.

## **12. ELIGIBILITY CRITERIA**

### **12.1. INCLUSION CRITERIA**

- a. Patients who will have deceased or living kidney donor transplants
- b. Patients aged 18 years or above.
- c. Patients able and willing to comply with the trial requirements

### **12.2. EXCLUSION CRITERIA**

- a. Patients who will have a kidney transplant with more than two arteries (evident at the time of surgery).
- b. Patients below 18 years of age.
- c. Patients lacking capacity or unwilling to give consent.

## **13. TRIAL SETTINGS**

Southwest transplant centre, University Hospitals of Plymouth NHS trust.

## **14. DURATION OF THE STUDY**

24 months

## **15. SAMPLE SIZE**

This is feasibility RCT; it is not compulsory to perform a formal power calculation. The sample size is chosen based on the practicalities of conducting a feasibility study. The sample size is a realistic recruitment figure for 24 months based on a recent retrospective study conducted at the Southwest transplant centre leading to this research project. The data suggested that about 65-70 kidney transplants were performed annually in our unit. After exclusion criteria, we anticipate that about 100 patients will be available for recruitment in two-year study duration. The data also suggests that in the last five years there were minimal number of kidney transplant patients that opted not to receive additional vascular monitoring or refused participation after their procedure. This allows us the reassurance of minimum dropout rates in the study.

The COVID-19 pandemic has resulted in an unprecedented increase in our kidney transplant activity. It is due to the reason that the Southwest region has remained the least affected in the UK and our transplant centre remained open. On the contrary, most transplant units across the UK had to be closed down due to infection and resource constraints. This led to the increased

diversion of organ resources to the Southwest transplant centre. As a result, our End-stage renal disease (ESRD) patients availed themselves of the opportunity of more graft offers than usual. This allowed us to perform more transplant surgeries as compared to previous years.

The randomised controlled feasibility trial aims to recruit 50 kidney transplant patients within a 24-month period; 25 in intervention group and 25 in control group. In our study, we propose to attach an implantable continuous vascular monitoring device to half (i.e. 25) of the kidney transplant patients (intervention Group) during their surgery. Postoperatively, these patients will receive graft surveillance by the monitoring device in addition to the standard care clinical observation. The other half (i.e. 25) of the kidney transplant patients (control Group) will receive the standard care clinical observation.

## 16. CONSENT

A kidney transplant is an urgent surgery as the deceased donor organs are offered by the NHS Blood and Transplant at 12-14 hours' notice. After the offer is accepted by the recipient transplant centre, the patient is called in. There is a waiting period of only 8-10 hours during which the recipient is consented and optimised for the surgery.

After the routine surgical consent, it will be the responsibility of the chief investigator (CI) to inform the patients about the study and invite them to participate. In case he is not present due to any emergency, the responsibility will be delegated to the on-call Transplant Consultant who is a regular part of the patient's clinical care team.

Consent to enter the study will be sought from each participant only after a full explanation of recruitment, randomisation, instructions elaborating on the functioning of the device, and allotment to intervention or control group has been given. The participants will be made aware that if they fall in the intervention group, they will have implantable Doppler probe monitoring in the first 72 hours after the surgery in addition to the standard care clinical observation. An information leaflet will also be offered, and time allowed for consideration that would be about six to eight hours. A duly signed informed consent form will be obtained from patients that agree to participate in the study.

All participants will be made aware that they can withdraw from the study anytime from when they give consent to participate till the first 72 hours after the surgery at which the monitoring device will be removed. This will be done regardless of their allotted group, without giving reasons, and prejudicing their treatment. They will also be informed that they have the option to not participate in the study without any change in their postoperative care. The right of a patient to refuse participation in the study without giving reasons will be respected.

All the potential kidney transplant patients are assessed thoroughly at the Southwest transplant centre before activating them on the transplant waiting list. If there is a requirement for special communication needs (i.e. language barrier), an interpreter will be arranged in advance.

## 17. RANDOMISATION

The patients who consent to participate in the study will be randomised into two groups (i.e. intervention and control) by a secure online computer sequence generator system (<https://www.randomizer.org/#randomize>). Randomisation will be completed in a 1:1 ratio using random permuted blocks. Randomisation will be the responsibility of the delegated on-call Transplant Consultant.

The patients allotted to the Intervention group will have kidney transplants with the implantable continuous vascular monitoring device while those allotted to the Control group will have kidney transplants with standard care clinical observation (i.e. without implantable continuous vascular monitoring device). Following kidney transplant surgery, all patients will be managed in the standard way followed at the Southwest transplant centre as per the Trust protocol.

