### 20.1. PARTICIPANT'S DEMOGRAPHIC CHARACTERISTICS

- a. Age at the time of operation in years and months (not the date of birth), gender, and BMI.
- b. Cause of renal deterioration.
- c. Dialysis modality at the time of transplantation
- d. Time on the kidney transplant waiting list
- e. Source of the donated kidney (living versus deceased donor)
- f. Prior renal transplant
- g. Surgeon undertaking the procedure (coded to maintain anonymity)
- h. Recipient risk factors for transplant surgery (age > 70 years, BMI > 30, cardiovascular disease, smoking, peripheral vascular disease, thromboembolic disease, hypertension (HTN), diabetes mellitus (DM), and urological obstructive symptoms)
- i. Donor risk factors for transplant surgery (Donor age > 60 years, BMI > 30, cardiovascular disease, smoking, peripheral vascular disease, hypertension (HTN), diabetes mellitus (DM), cold ischemia time (CIT), cause of death, HLA mismatch, and the number of vessels on the graft).

**20.2. OUTCOME MEASURES FOR OBJECTIVE 1:** To assess the capability of vascular monitoring device in the early postoperative care of kidney transplant patients.

- a) The number of early vascular complications identified and their management (incidence).
- b) The period between the graft implantation and diagnosis of vascular complication (early or late).
- c) The number of departmental ultrasound scans requested by the clinicians taking care of the patients in the first 24, 48, and 72 hours postoperatively.
- d) The 03-month kidney graft survival (the number of grafts lost due to vascular complications in the first 03 months).

**20.3. OUTCOME MEASURES FOR OBJECTIVE 2:** To assess the research methods used to compare vascular monitoring device with the standard care and to estimate surgical outcome measures essential to inform the sample size calculation for the definitive planned RCT.

- a. Suitability of eligibility criteria and recruitment process.
- b. Refusal rates for participation and randomization
- c. Retention and follow-up rates during the research process

- d. Assessment of the study methods, procedures, and follow-up schedules (researcher and participants)
- e. Assessment of the procedures for monitoring variation and fidelity in the delivery of the intervention. A fidelity checklist will evaluate the adherence to the standardised protocol of intervention delivery (i.e. consent of the participants, delivery of the intervention, and conduct of the serial Doppler signal monitoring).

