### **22.1. PARTICIPANT'S DEMOGRAPHIC CHARACTERISTICS**

The participant's demographic or baseline characteristics in both groups will be summarised separately using descriptive statistics. The numerical data for both groups will be compared in the tabular form to demonstrate whether or whether not the participant's baseline characteristics in the Intervention and Control groups are identical.

**22.2. OUTCOME MEASURES FOR OBJECTIVE 1:** To assess the capability of vascular monitoring device in the early postoperative care of kidney transplant patients.

The first step will be to evaluate if the vascular monitoring device truly works in the sense of achieving its intended outcome (i.e. vascular monitoring in kidney transplant patients). According to the MRC Framework assessing a clear theoretical basis for the intervention is paramount for further evaluation of complex interventions . The percentages of the surgical outcomes in the Intervention and Control groups will be compared in tabular form. From this comparison, it will be noted whether the vascular monitoring device can safely identify vascular complications and prevent graft loss.

The relative risk or risk ratio for the surgical outcomes will also be calculated using the following formula.

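### Stratifying allocation by donor source would cheaply remove a roughly 3-20% chance that arms of 25 differ by 20 points or more in donor mix (optional improvement)

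*Protocol*

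**What the plan says.** - **Allocation.** Protocol section 17: "Randomisation will be completed in a 1:1 ratio using random permuted blocks". It gives no block size and no stratification factor. None appears elsewhere in the protocol, or in the document supplied as the SAP, which is a data management plan.
- **Size.** Section 15 plans "25 in intervention group and 25 in control group". No power calculation lies behind this: "The sample size is chosen based on the practicalities of conducting a feasibility study".
- **Who enters.** Section 12.1 admits "Patients who will have deceased or living kidney donor transplants".
- **When donor source is known.** Section 16 explains that "deceased donor organs are offered by the NHS Blood and Transplant at 12-14 hours' notice". The offer precedes admission, and consent and randomisation follow, so the type of donor is settled before allocation. The documents imply this and do not state it.
- **What is recorded.** Section 20.1, item e: "Source of the donated kidney (living versus deceased donor"). Item i is a separate list of donor risk factors that includes cold ischaemia time and cause of death.
- **What is compared.** Objective 1 covers vascular complications, time to their diagnosis, ultrasound scans over 72 hours and three-month graft survival. On scans, section 10 says that the clinician "may request additional departmental ultrasound scans in the first 72 hours depending on the graft function" and on the recipient's condition. Section 22.2 compares raw percentages by arm, with a risk ratio and a risk difference, and no adjustment or subgroup display.

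**The concern.** A single blocked list keeps the arm totals close and leaves everything else to chance. With 25 per arm, chance can produce a visible difference in the proportion of living-donor grafts. If donor source is related to early graft function, that difference feeds into scan requests and perhaps into complications and graft loss. It would then be mixed into the device comparison.

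This matters more than it might in a purely operational feasibility study. Section 22.2 intends to read from the table whether the device detects complications safely and saves grafts. Section 20.3, item g, intends to carry between-arm differences into the sample size of the definitive trial. The baseline table in section 22.1 would reveal an imbalance in donor source, but nothing in the analysis would deal with it.

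**Working it through.** **Plan's own figure.** The only one on this point is the sample size: 25 + 25 = 50, which agrees. The plan states no power, donor mix or imbalance figure.

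**Step 1. Chance of imbalance on an unstratified list.** Inputs are 25 per arm (section 15) and a share *p* for the less common donor type. The documents do not give *p*, so it is varied from 10% to 50% as an assumption. A 20-point difference is 0.20 × 25 = 5 patients. Treat the two arms' counts as independent Binomial(25, *p*) and sum the joint probabilities over all pairs that differ by 5 or more. The standard deviation of the difference is √(2*p*(1−*p*)/25).

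| Share *p* | SD (points) | P(difference ≥ 20 points, either direction) |
|---|---|---|
| 10% | 8.5 | 3.4% |
| 15% | 10.1 | 7.3% |
| 20% | 11.3 | 11.0% |
| 30% | 13.0 | 16.4% |
| 40% | 13.9 | 19.3% |
| 50% | 14.1 | 20.3% |

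Hand check at 30%: SD = √(2 × 0.3 × 0.7/25) = 0.130. The continuity-corrected normal value is 2 × [1 − Φ((0.20 − 0.02)/0.130)] = 16.5%, which agrees.

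**Step 2. Does blocking alone help?** Unstratified permuted blocks of 2, 4 and 6 were simulated with 10,000 runs per setting. The chance was 9-11% at *p* = 20%, 15-16% at 30% and 18-20% at 40%. That is close to the table, so blocking on its own does little for donor mix.

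**Step 3. Blocks within donor type.** In the same simulations with separate lists for living and deceased donors, no run reached 20 points. The largest imbalance seen was 4 points with blocks of 2, about 8 with blocks of 4 and about 12 with blocks of 6. The total stays at 50.

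**Step 4. What a 20-point imbalance would do to graft loss.** Section 6.2 gives early graft loss of 7-10%, of which 30-35% is vascular. That makes vascular loss 0.07 × 0.30 = 2.1% to 0.10 × 0.35 = 3.5%. Assume a living share of 30% and a deceased-to-living risk ratio RR of 1.5 to 3; neither figure is in the documents. With overall risk *r*:

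- living-donor risk = *r* / (0.3 + 0.7 × RR)
- deceased-donor risk = RR × living-donor risk
- shift in the risk difference = 0.20 × (deceased-donor risk − living-donor risk)
- standard error of the risk difference = √(2*r*(1−*r*)/25)

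Example: *r* = 10% and RR = 3 give a living-donor risk of 0.10/2.4 = 4.17% and a deceased-donor risk of 12.5%. The shift is 0.20 × 8.33 = 1.67 points, and the standard error is √(2 × 0.10 × 0.90/25) = 8.5 points.

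| Outcome | Shift (points) | Standard error (points) |
|---|---|---|
| Early graft loss, 7-10% | 0.5-1.7 | 7.2-8.5 |
| Vascular graft loss, 2.1-3.5% | 0.2-0.6 | 4.1-5.2 |

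**Step 5. Scan counts.** The documents give neither a scan rate nor a variance, so no shift can be calculated.

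**The case against.** The strongest reply is that this is a 50-patient, single-centre feasibility trial with descriptive analysis. Chance imbalance does not bias randomisation, donor source will be tabulated by arm, and on Step 4 the graft-loss comparison is dominated by sampling noise whether or not the list is stratified. All of that stands, and it is why the point is optional. Other listed factors, such as prior transplant and surgeon, could also be proposed, and the documents do not rank them. Donor source is the suggestion because it is binary and known at allocation. Choosing it remains a judgement.

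Three stronger readings are tempting and are not supported:

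- *Donor source is shown to affect the outcomes.* No passage says so. Section 20.1 lists it apart from the donor risk factors, and no event rate by donor type is given. The support is indirect: cold ischaemia time and cause of death are listed as donor risk factors, and scan requests depend on graft function.
- *The risk is 22%.* Fixing the number of living-donor recipients at exactly 15 of 50 gives 21.7%, but 14 gives 11.4% and 16 gives 12.8%. With 25 per arm the difference must be odd when that number is odd and even when it is even. A threshold of 5 therefore acts as 6 for even numbers. The binomial values average over this.
- *Section 22.1 sets a standard that the arms must meet.* The phrase "baseline characteristics in the Intervention and Control groups are identical" is loose, since randomised arms hardly ever are. But the section describes a table with no test or decision attached, so this is only a matter of wording.

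Stratifying would also not repair section 22.2's reading of a device effect from raw percentages. That is a separate problem of interpretation.

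**Conclusion.** The point holds as a modest design improvement. A factor that is known before allocation and recorded at baseline is left to chance, and the arms are then compared unadjusted. The chance of a 20-point or larger imbalance in donor mix is about 3% if the less common donor type is 10% of recruits, 11% at 20%, 16% at 30% and 20% at 50%. Small blocks within donor type make it essentially nil.

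These figures assume exactly 25 per arm. Exclusions found at surgery under section 12.2 would alter them slightly. The donor share is an assumption throughout, and the risk ratios used to size the consequence are assumptions too.

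A reader might infer that the graft-loss comparison would be seriously distorted. The calculation does not support that: the shift is a small fraction of the standard error. The case rests more on scan counts, which the protocol ties to graft function, and there the size is unknown. No statement or figure in the plan is wrong. Priority: optional.

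**What to change.** In section 17, write: *Randomisation will use random permuted blocks stratified by donor source (living, deceased).* Keep the blocks small.

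In the Objective 1 results, show scan counts by donor source within arm, descriptively. Splitting graft loss the same way would add little: 2.1-3.5% of 50 is only about one or two vascular losses in the whole trial.

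**Cost.** Two allocation lists instead of one, and one extra table. The sample size stays at 50. The final split may be slightly uneven: with blocks of 4 in two strata the worst case is 26/24. A single list in blocks of 4 can also end there, because 50 is not a multiple of 4. If allocation has already started, the change to the list may no longer be practical, but the table can still be added.

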## **18. TRIAL ARMS**

### **18.1. INTERVENTION GROUP (KIDNEY TRANSPLANT PATIENTS WITH THE IMPLANTABLE CONTINUOUS VASCULAR MONITORING DEVICE)**

The intervention that is intended to be investigated is the implantable continuous vascular monitoring device manufactured by COOK Medical Company. Its principle intended use is continuous monitoring of the graft perfusion (i.e. transplanted kidney) for the first 72 hours postoperatively. The kidney transplant patients in the intervention group will receive implantable continuous vascular monitoring device surveillance for the first 72 hours in addition to the standard care clinical observation as part of their postoperative care.

The continuous audible Doppler signals produced by the monitoring device represent the blood flowing in the renal artery. This is an indicator of graft perfusion. Cessation of audible Doppler signals is the key that may suggest hampered blood flow due to vascular complications. In the intervention group, the monitoring device will be used as an added mechanism to monitor graft perfusion. Theoretically, the vascular complications should be identified early, the patients should undergo prompt surgical correction, and better outcomes with less graft loss should be noted in the intervention group as compared to the control group. This scientific basis of the intervention will be tested in this study.

The audible Doppler signals representing the graft perfusion will be monitored continuously by the transplant surgeon till the wound closure in the theatre. In the recovery, the signals will be monitored continuously by the duty nurse till the time patient is transferred to the ward. After that, it will be monitored intermittently as required by the clinician on call in the ward.

The vascular monitoring device is already in use at our hospital by the plastic and reconstructive surgery department, so we do not anticipate any administrative problems with the use of this device. The host renal ward has already trained the nurses and funds have already been allocated to acquire the monitoring devices for the duration of the study. The removal of the monitoring device is a simple and uncomplicated procedure. It will be undertaken 72 hours postoperatively by the duty nurse looking after the patient.

### **18.2. CONTROL GROUP (KIDNEY TRANSPLANT PATIENTS WITH STANDARD CARE CLINICAL OBSERVATION):**

The kidney transplant patients in this group will receive the standard care clinical observation as part of their postoperative care. Their graft will be monitored postoperatively by the standard care clinical observation as per the NHS protocol.

## **19. BLINDING**

Blinding of the participants (kidney transplant patients) to the outcome of the randomisation will not be possible due to the nature of the intervention. Similarly, the healthcare professionals (clinicians and nurses) taking care of the patients and collecting the data postoperatively cannot be blinded. However, the Southwest transplant team acts in the best interest of the kidney transplant patients and declares no conflict of interest with the device.

